In Session 1 (pre-medication baseline), we will collect baseline measures of smoking urge, withdrawal symptoms, mood, cognitive performance, a behavioral economics-based measure of cigarette demand and effects of smoking a cigarette on cigarette reward, satisfaction and mood. Next, participants will be randomized to VAR (1 mg twice daily for 3 weeks) or PLA, using urn randomization to stratify on gender and dependence. Participants will complete a week of medication use using the standard dose run-up (0.5 mg once daily on days 1-3, 0.5 mg twice daily on days 4-7, then 1 mg twice daily until the end of the medication period). In Session 2, which occurs after one week on medication, participants will complete the same laboratory assessments as in Session 1. Next, participants will undergo a 3-day abstinence period. They will come to the laboratory twice per day and will receive escalating cash incentives for breath carbon monoxide (CO)-verified abstinence. At each visit, cigarette craving and withdrawal symptoms will be measured. At Session 8 (Thursday morning), participants who have been continuously abstinent will complete the same procedure as in Sessions 1. For ethical reasons, participants who complete the study through Thursday and who wish to remain abstinent may opt out of smoking during this session and will still receive full compensation for participation, as long as they attend this lab session and complete the other session measures.

Participants will be asked to return to the laboratory on Friday morning. Breath CO will be measured and time of first lapse (single cigarette) and relapse (return to regular smoking) will be collected among those who have lapsed and relapsed. Those still abstinent ($CO \leq 4$ ppm) since Session 8 will receive a small cash incentive. Next, participants will be shown how to use breath CO monitors with smart phones to record

and text us videos of themselves providing CO samples twice per day for the following week to determine time to lapse and relapse. Participants will receive \$5 for each submitted sample (not contingent on CO level), paid when the smart phone and CO monitor are returned at the end of the week.

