- 2) **Breach of Confidentiality**: The risk of the interview is loss of privacy if other people find out the results. We will work to ensure that the participant's confidentiality is kept, and a Certificate of Confidentiality will be obtained from NIDA to further protect confidentiality. Study data will be identified only by numeric code and stored in locked file cabinets, or on password-protected computers. A master list of participant names and contact numbers will be kept completely separate from other information about participants in order to facilitate study visit scheduling and coordination. Only those with a need to know (for assessments of adverse events) or mandated auditors will have access to the master list linking names and code numbers. Clinically important assessment data such as new concomitant medications or adverse events will be made available to the medical monitor so that he can evaluate the participant coordinate an effective response. All study staff have received (and new staff will receive) mandatory human subjects' protections training. All are highly experienced with relevant ethical principles, particularly around confidentiality. Digital video files of CO samples will be deleted once these data have been coded.
- 3) **Coercion**: Coercion can arise from the payments that participants can earn for participation. Payments are considered compensation for assessment and travel time, and the rate is consistent with local standards for research. The R21 study includes high-value cash incentives for abstinence, which is necessary for experimentally-controlling smoking abstinence in this study as we demonstrated in a previous study (Tidey et al., 2014). Participants are free to discontinue at any time and will receive compensation for the sessions that they complete at the same rate and in the same form as those who complete that study. As an added protection for participants, those who initiate and maintain abstinence in this study through Thursday and wish to remain abstinent can opt out of the post-abstinence smoking assessment and still receive full compensation, as long as they attend the visit for the same amount of time as those who smoke and complete the other assessments. The R33 study includes a contingency management (CM) system, in which participants will receive voucher-based incentives for abstinence. Incentive values are in line with those offered in other CM studies for smoking cessation (e.g., Dallery et al., 2013).

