
- 4) Nicotine Withdrawal: Participants may experience some discomfort when abstaining from smoking. Symptoms can include irritability, frustration, anxiety, depressed mood or sadness, desire or craving to smoke, difficulty concentrating, and increased appetite or hunger. These feelings can be uncomfortable but they are normal, temporary, and usually mild.
- 5) Effects of Varenicline (VAR): The results of the largest study to date of varenicline's efficacy and safety in smokers with and without psychiatric disorders found no increase in neuropsychiatric adverse events attributable to varenicline relative to nicotine patch or placebo (Anthenellie et al., 2016). The most frequent adverse event associated with varenicline is mild to moderate nausea, occurring in 25-45% of users, diminishing over time, and not leading to varenicline discontinuation (Anthenelli et al., 2016; Cahill et al., 2009; Ebbert et al., 2010; Evins et al., 2014; Leung et al., 2011). Other common adverse events include insomnia, abnormal dreams and headaches; serious adverse events have been rare in randomized, controlled phase III studies, and there have been no treatment-related deaths and no known contraindications (Anthenelli et al., 2016; Aubin et al., 2014; Evins et al., 2014). Nevertheless, patients receiving VAR should and will be monitored in this study for changes in psychiatric symptoms including mood and suicidality. Co-Investigators [name], a licensed clinical psychologist, and [name], an addictions psychiatrist, will assess and assist with any participants who experience increases in psychiatric symptoms during the study. We will ask participants to sign a medical release form that will allow us to inform their psychiatrist or other healthcare provider that they are participating in a research study in which they may be receiving VAR under double-blind conditions.

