- 6) Changes in Psychiatric Symptoms Secondary to Changes in Smoking Behavior. Changes in smoking can affect how well some psychiatric medications work due to changes in CYP1A2 enzyme activity. We believe the risks of these events are low given the low incidence of such changes in clinical trials, including a trial that included over 4000 smokers with psychiatric disorders (Anthenelli et al., 2016; Evins et al., 2014). However, we will inform participants about these risks and ask participants to provide us with written permission to notify their treating clinician that they are in a study in which they may receive VAR and a behavioral treatment (R33 phase only) that may affect their smoking rate. Adverse events will be collected weekly using a checklist and open-ended questions. In addition, psychiatric symptoms will be assessed with the BPRS and Calgary Scale at every in-person session and movement disorders will be assessed with the AIMS, Simpson-Angus Scale and BARS at the screening and last session. Moderate-to-severe increases in symptoms (e.g., change from mild/moderate category to severe) will trigger review by [name] or [name], who will meet with the participant if needed. Serious adverse events and unexpected related adverse events will be reported to the Brown University IRB as noted above (see **Regulatory Issues** section). Participants will be given contact information so that they can reach the PI, [name], [name], or study staff at any time to report adverse events. Participants reporting suicidal intention at any time (score ≥ 4 on the Columbia Suicide Severity Rating Scale, suicide plan endorsed on the Calgary Depression Scale for Schizophrenia, or spontaneous reports) will be put in contact with [name] or [name] immediately. The clinician will speak with the participant in person if suicidality is reported during a study visit or by phone if it is reported by phone. The clinicians will then determine the next steps to be taken. Having 2 clinicians on this study increases the likelihood that at least one will be available. However, if neither is available, other qualified clinicians at our research center will speak with the participant. The PI will follow any steps recommended by the clinician (i.e., to continue or discontinue participation).

Potential benefits of participation

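### As described, the R21 notice to treating clinicians omits the paid 3-day smoking abstinence planned in both medication groups

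*Combined protocol and SAP*

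**What the plan says.** Potential risks of participation, item 6, deals with psychiatric changes that follow from changes in smoking. It gives the mechanism: "Changes in smoking can affect how well some psychiatric medications work due to changes in CYP1A2 enzyme activity". It then sets out safeguards. Participants are told of the risk, and the study asks for written permission to inform the treating clinician. The plan words the notice as follows: "notify their treating clinician that they are in a study in which they may receive VAR and a behavioral treatment (R33 phase only"). The sentence closes with a clause on smoking, so that its last element is "a behavioral treatment (R33 phase only) that may affect their smoking rate". The same item gives the plan's view of the hazard: "We believe the risks of these events are low given the low incidence of such changes in clinical trials".

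Item 5, on the effects of VAR, describes a medical release form that lets the study tell the psychiatrist or other provider that the person is "participating in a research study in which they may be receiving VAR under double-blind conditions". It says nothing about abstinence.

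The R21 procedure is in Brief Description of Protocol. After Session 2, with no distinction between medication groups, "participants will undergo a 3-day abstinence period. They will come to the laboratory twice per day and will receive escalating cash incentives for breath" CO-verified abstinence. Those who reach Session 8 and want to stay abstinent may decline the smoking part of that session. A small further incentive is paid on Friday to those still abstinent. Item 3 (Coercion) confirms the intent: "The R21 study includes high-value cash incentives for abstinence", which it justifies as needed to keep abstinence under experimental control.

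**The concern.** The hazard in item 6 is change in smoking, not VAR as such, and notifying the clinician is one of the plan's chosen safeguards against it. R21 deliberately brings about a complete stop in smoking for 3 days in both groups. The notice as described for R21 mentions a possible drug and leaves that stop out. The two parts of the plan do not fit together.

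At stake is what the clinician who manages the psychiatric medication knows. Someone told only that a patient may be taking VAR would not know that a period of abstinence is planned, or that it is planned for a placebo participant just as much. This is a participant-safety matter about the content of a notice. What a clinician does with the information is outside the point.

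**Working it through.** The point rests on text, and no statistic of the plan depends on it. The R21 procedure and the R21 notice compare as follows.

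| Element | R21 procedure (Brief Description of Protocol; item 3) | R21 notice as described (items 5 and 6) |
|---|---|---|
| Possible VAR | Yes | Stated in both items |
| Smoking rate may change | Yes, by design | Item 5: no. Item 6: on one reading only, and tied to VAR |
| Planned 3-day abstinence after Session 2 | Yes, paid and CO-verified | Not mentioned |
| Applies whichever capsule is assigned | Yes | Not mentioned |
| Participant may stay abstinent afterwards | Yes | Not mentioned |

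The second row depends on how the sentence in item 6 is parsed once the R33-only part is set aside.

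- **Reading A.** The closing clause about smoking rate belongs to the behavioral treatment alone. The R21 notice then says only that the participant may receive VAR, which agrees with item 5.
- **Reading B.** The clause belongs to VAR as well. The R21 notice then says that the participant may receive VAR and that VAR may affect smoking rate.

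Under both readings the planned abstinence is absent. Under Reading B, the only source of smoking change named to the clinician of a placebo participant is a drug that the participant is not taking.

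Number of people concerned, from Power Calculation and Sample Size:

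- R21: 60 enrolled less 20% gives 60 × 0.80 = 48 randomized. At 30 enrolled per group, 30 × 0.80 = 24 per medication group, so about 24 are on placebo.
- The abstinence period follows Session 2, so 48 is an upper limit. Anyone who leaves before that point is not exposed to it.

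**The case against.** Several points on the other side stand.

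**The R33 label is accurate.** R21 is a laboratory model, and its incentives are a means of experimental control. The contingency management intervention belongs to R33. The fault is an omitted procedure, not a wrong phase. Deleting the R33 limit would make the R21 notice announce a treatment that R21 does not give.

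**Clinicians may be told that smoking could change.** A reader might infer that R21 clinicians hear nothing about smoking. Reading B does not allow that to be said outright. The notice and release form are also described here, not reproduced, so their actual wording cannot be checked.

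**Other safeguards exist.** A reader might infer that protection fails in R21. The documents do not support that. Item 6 informs participants and schedules the BPRS and Calgary Scale at every in-person session, with review by study clinicians of moderate-to-severe increases. R21 visits are twice daily during abstinence. Collection and reporting of AEs and SAEs has adverse events and concomitant medications assessed at every visit. A dose change in chronic medication within 30 days is an exclusion. These do not put the planned abstinence before the treating clinician, but they mean that the notice is not the only protection.

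**Comparing the phases proves little.** A reader might note that abstinence-contingent payment reaches 48 of 48 people in R21 but 48 / 3 = 16 of 48 in R33, and conclude that the notice is fuller in the less exposed phase. Duration reverses this. Taking Weeks 2-5 as 28 days, with equal arms and no dropout, R21 has 48 × 3 = 144 person-days (48 × 4 = 192 if Friday is counted) and R33 has 16 × 28 = 448. The omission matters because of what R21 does, not because R21 exceeds R33.

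**Bias in the data is not shown.** A reader might infer that an uninformed clinician distorts the psychiatric or adverse-event data. The study collects those data itself, and nothing in the documents traces such an effect.

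**Conclusion.** The narrow point holds: items 5 and 6 describe an R21 notice that does not mention the incentivised, CO-verified 3-day abstinence applied in both medication groups, although item 6 treats smoking change as the source of the risk. It should be put right because the safeguard is the plan's own and the correction is small.

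Its reach is up to 48 planned R21 participants, about 24 on placebo if groups are equal, for a planned period of 3 days. Its clinical size cannot be stated. The plan says only that smoking change can affect some medications, rates the risk as low, and gives no figure for the effect of 3 days of abstinence. No claim is made that the other safeguards fail or that the trial's results are biased. The conclusion assumes that the notice follows its description in items 5 and 6. If the forms in use already cover the abstinence period, only those two descriptions need correcting.

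**What to change.** Reconcile items 5 and 6 of Potential risks of participation with Brief Description of Protocol and item 3. Keep the R33 limit on the behavioral treatment. Add an R21 clause to the release form and the notice, and to their descriptions in items 5 and 6, saying that:

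- the study includes a planned 3-day smoking abstinence period after Session 2;
- it applies whichever capsule is assigned; and
- the participant may remain abstinent afterwards.

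The clause need not mention payment.

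The notice still depends on the participant's written permission. When editing, align this with the Quality Assurance section, which shares information with clinicians only at the participant's written request, whereas items 5 and 6 have the study ask for permission.

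The cost is one sentence and an IRB wording amendment, with no added visits, staff or data collection.

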This Board will meet at regular intervals (every 6 months) to evaluate the progress of the trial, data quality, recruitment, participant demographics, study retention, and other factors that may affect study outcome. This meeting will be conducted as a conference call. Included in the review will be protocol violations, quality of data collection, overall data flow and study drop outs and reasons. The Board will also review the participants' ability to achieve study requirements and the rates of adverse events to assess trends and determine whether there has been any change in participant risk. The DSMB will review all serious or unexpected adverse events and provide recommendations. The review will ensure that subject risk does not outweigh the study benefits. A brief report will be generated from each of these meetings for the study record and forwarded to the Brown Institutional Review Board (IRB) and to the NIDA Program Officer with the progress report.

The DSMB will be available to convene outside of the regular meetings, if necessary. If concerns should arise regarding a particular subject, or any troublesome trends in the experiences of participants, they will make appropriate recommendations for changes in protocol, as needed.

Conflicts of interest

No board members will be affiliated with the grant other than through their work on the board. Each member will complete a conflict of interest disclosure form prior to each meeting. Ad hoc specialists may be invited to participate as non-voting members at any time if additional expertise is desired.

Protection of confidentiality

During DSMB meetings, only de-identified data, including blinded study site and condition type, will be provided to the board. All data and discussion during the meeting will be confidential.

Monitoring activities (initial and ongoing study review)

The DSMB's charge will include evaluating the standard procedures for monitoring developed by the investigators. The DSMB will begin by reviewing the study protocol and data and safety monitoring plan. This review will include protocol design, the appropriateness of the inclusion/exclusion criteria, the randomization plan, the definition of participants (e.g., screened, enrolled, randomized, treated, drop out, lost to follow-up), assessment and subjective measures and study biomarkers. The DSMB will ultimately establish the criteria for safety concerns, discontinuing a participant, and how to deal with missing visits/data.

